2.3.1. Risk Assessment

Potential Risk of Clinical Significance	Summary of Data/Rationale for Risk	Mitigation Strategy							
	Study Intervention(s) PF-07817883								
CCI									

2.3.2. Benefit Assessment

For healthy participants in this study, no clinical benefit is expected.

2.3.3. Overall Benefit/Risk Conclusion

PF-07817883 is not expected to provide any clinical benefit to healthy participants in this study.

Taking into account the measures to minimize risk to study participants, the potential risks identified in association with PF-07817883 are justified by the anticipated benefits that may be afforded to participants with COVID-19 in future.

3. OBJECTIVES AND ENDPOINTS

Objectives	Endpoints			
Primary:	Primary:			
To determine the oral bioavailability of test oral formulations of PF-07817883 relative to the reference oral formulation.	C _{max} and AUC _{inf} if data permit, otherwise AUC _{last} .			
Secondary:	Secondary:			
To evaluate the safety and tolerability of PF-07817883 formulations in healthy participants.	Assessment of TEAEs, clinical laboratory abnormalities, vital signs, and 12-lead ECGs.			
Tertiary/Exploratory:	Tertiary/Exploratory:			
To characterize the PK of PF-07817883 after single oral dose of PF-07817883 formulations.	 Plasma PK parameters: T_{max}, C₁₂, and if data permit V₂/F, CL/F and t_{1/2}. 			
To assess the drug product acceptability of PF-07817883 formulations.	Assessment of drug product acceptability via a questionnaire.			

4. STUDY DESIGN

4.1. Overall Design

This is a Phase 1, open-label, randomized, 4-period, 4-sequence crossover study in healthy adult participants evaluating the rBA of 3 new PF-07817883 test oral formulation(s) compared to PF-07817883 reference oral formulation. Approximately 12 participants will be enrolled in this study with approximately equal number of participants randomized to 1 of 4 sequences (Table 2). The new formulations used for each treatment as defined in Table 2 will be decided based on the availability of new formulations.

Table 2. Study Design

Sequence	Period 1	Period 2	Period 3	Period 4
1 (n=3)	A	В	C	D
2 (n=3)	В	D	A	C
3 (n=3)	C	A	D	В
4 (n=3)	D	С	В	A

Treatment A = PF-07817883 300 mg reference formulation, fasted, DP-006067, 23-DP-01449

Treatment B = PF-07817883 300 mg test formulation 1, fasted, DP-006067, 23-DP-01526

Treatment C = PF-07817883 300 mg test formulation 2, fasted, DP-006973, 23-DP-01687

Treatment D = PF-07817883 300 mg test formulation 3, fasted, DP-006974, 23-DP-01696

Healthy participants will be screened to determine eligibility within 28 days prior to study treatment. Participants will report to the CRU on Period 1 Day -1 (Study Day -1) and will be required to stay at the CRU until discharge. The participants will remain confined at the CRU until all assessments in all periods are complete.

In each period on Day 1, following an overnight fast of ~10h, participants will receive one of the treatments as defined in Table 2. Serial plasma PK samples will be collected up to 48 hours following the dose, at times outlined in the SoA. Participants will also complete a drug-product acceptability questionnaire shortly after receiving PF-07817883 in each period. At least 48 hours of washout between the doses of PF-07817883 administered to a participant in consecutive periods will be implemented. Dosing in the subsequent periods can take place immediately following the last PK sample collection of a period (SoA, Section 5.3).

A follow-up (which may be a phone call) will be made to participants approximately 28 to 35 days from administration of the final dose of study intervention.

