1.2. Schema

Figure 1. Schema

DMID, lot numbers:

A: DP-006067, 23-DP-01449 B: DP-006067, 23-DP-01526 C: DP-006973, 23-DP-01687 D: DP-006974, 23-DP-01696

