6.1. Study Intervention(s) Administered

Study Intervention(s)					
Intervention Name	PF-07817883				
Туре	Drug				
Use	Experimental				
IMP or NIMP/AxMP	IMP				
Dose Formulation	All test formulations and the reference formulation are immediate release tablets and expected have similar performance. All tablet formulations are of 300 mg unit strength.				
Unit Dose Strength(s)	300 mg/ tablet				

Study Intervention(s)					
Dosage Level(s) 300 mg single dose per treatment, per period.					
Route of Administration	Oral				
Sourcing	Provided centrally by the sponsor				
Packaging and Labeling	Study intervention will be provided in bulk. CRU staff will prepare individual doses for administration. Each dose container will be labeled as required per country requirement.				
SRSD	IB for PF-07817883				
Current/Former Name(s) or Alias(es)	PF-07817883				

Study Arm(s)								
Arm Title	A	В	С	D				
Arm Description	Participants will receive 300 mg SD of reference formulation on Day 1 of the treatment period	Participants will receive 300 mg SD of test formulation 1 on Day 1 of the treatment period	Participants will receive 300 mg SD of test formulation 2 on Day 1 of the treatment period	Participants will receive 300 mg SD of test formulation 3 on Day 1 of the treatment period				
DMID, Lot	DP-006067, 23-DP- 01449	DP-006067, 23-DP- 01526	DP-006973, 23-DP- 01687	DP-006974, 23-DP- 01696				

PF-07817883 will be supplied by Pfizer as 300-mg tablets.

Tablets will be supplied to the CRU in bulk along with individual dosing containers for unit dosing.

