6.5. Study Intervention Compliance

When the individual dose for a participant is prepared from a bulk supply, the preparation of the dose will be confirmed by a second qualified member of the study site staff.

When participants are dosed at the site, they will receive study intervention directly from the investigator or designee, under medical supervision. The date and time of each dose administered in the clinic will be recorded in the source documents and recorded in the CRF. The dose of study intervention and study participant identification will be confirmed at the time of dosing by a member of the study site staff other than the person administering the

study intervention. Study site personnel will examine each participant's mouth to ensure that the study intervention was ingested.

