9.2. Analysis Sets

For purposes of analysis, the following analysis sets are defined:

Participant Analysis Set	Description	
Enrolled	"Enrolled" means a participant's, or their legally authorized representative's, agreement to participate in a clinical study following completion of the informed consent process and randomization to study intervention.	
Safety analysis set	All participants randomly assigned to study intervention and who take at least 1 dose of study intervention in at least one treatment period. Participants will be analyzed according to the product they actually received.	
PK Concentration	The PK concentration population is defined as all participants	
analysis set	randomized and treated who have at least 1 concentration value in at least 1 treatment period.	
PK Parameter analysis	The PK parameter analysis population is defined as all	
set	participants randomized and treated who have at least 1 of the	
	PK parameters of interest in at least 1 treatment period.	

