4. ANALYSIS SETS (POPULATIONS FOR ANALYSIS)

Data for all participants will be assessed to determine if participants meet the criteria for inclusion in each analysis population prior to unblinding and releasing the database and classifications will be documented per standard operating procedures.

Participant Analysis Set	Description
Enrolled	"Enrolled" means a participant's, or their legally authorized representative's, agreement to participate in a clinical study following completion of the informed consent process and randomization to study intervention.
Safety analysis set	All participants randomly assigned to study intervention and who take at least 1 dose of study intervention in at least one treatment period. Participants will be analyzed according to the product they actually received.
PK Concentration analysis set	The PK concentration population is defined as all participants randomized and treated who have at least 1 concentration value in at least 1 treatment period.

Participant Analysis Set	Description
PK Parameter analysis set	The PK parameter analysis population is defined as all participants randomized and treated who have at least 1 of the PK parameters of interest in at least 1 treatment period.

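### Does the DMID shared by reference A and test formulation 1 leave the B versus A comparison open to mislabelling?

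*Protocol*

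**What the plan says.** Protocol 4.1 (Table 2) lists the reference as "Treatment A = PF-07817883 300 mg reference formulation, fasted, DP-006067, 23-DP-01449" and the first test product as "Treatment B = PF-07817883 300 mg test formulation 1, fasted, DP-006067, 23-DP-01526". The schema in Protocol 1.2 repeats the pairing: "A: DP-006067, 23-DP-01449 B: DP-006067, 23-DP-01526". The arm table in Protocol 6.1 and Table 2 of SAP 2.3 agree. Treatments C and D have DMIDs DP-006973 and DP-006974. Strength does not separate the arms either: "All tablet formulations are of 300 mg unit strength".

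On the dosing record, Protocol 6.5 says "The date and time of each dose administered in the clinic will be recorded in the source documents and recorded in the CRF". On the check at the bedside it says "The dose of study intervention and study participant identification will be confirmed at the time of dosing".

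On analysis sets, Protocol 9.2 and SAP 4 add one sentence to the safety set: "Participants will be analyzed according to the product they actually received". The PK sets have no counterpart. The PK parameter set reads "The PK parameter analysis population is defined as all participants randomized and treated who have at least 1 of the PK parameters of interest", with the condition that this holds in at least one period.

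Protocol 4.1 and SAP 2.3 also say that the choice of new formulation for each treatment depends on what is available, although the table beneath already lists a DMID and a lot for every treatment.

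**The concern.** Protocol 4.2 describes all three test products as new tablets compared with the current one, yet B has the current product's DMID and the visible text does not explain why. If only the lot distinguishes A from B, one would want the lot on the dosing record and a stated rule for PK data from a period in which the wrong product was given. Neither is written down. The SAP code in Appendix 1 uses a treatment variable without saying whether it is planned or actual.

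B versus A is one of three primary contrasts, and the results are meant to guide the choice of formulation. With about 12 participants and as few as 8 completers, one mislabelled pair carries weight. An exchange would pull the ratio towards 1, so the two products would look more alike than they are. The availability sentence adds to the unease because, read literally, it leaves the identity of B, C and D open.

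**Working it through.** **1. Identifiers.** From Protocol 4.1, Table 2:

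| Treatment | DMID | Lot |
|---|---|---|
| A (reference) | DP-006067 | 23-DP-01449 |
| B (test 1) | DP-006067 | 23-DP-01526 |
| C (test 2) | DP-006973 | 23-DP-01687 |
| D (test 3) | DP-006974 | 23-DP-01696 |

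There are four treatments, four lots and three DMIDs; A and B are the only pair that share one. The assignment is the same in the Protocol schema, Protocol Table 2, the Protocol 6.1 arm table and SAP 2.3, so the documents do not contradict each other. Appendix 9 expands DMID only as dosage material identification. Nothing says that a DMID must be unique to a formulation.

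**2. Sample size.** Protocol 9.5 gives 3 per sequence randomised and about 2 per sequence completing. With 4 sequences, 4 × 3 = 12 and 4 × 2 = 8, as stated. The within-participant standard deviations are blacked out, so the precision table cannot be reproduced. No figure in it is in dispute.

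**3. Effect of one exchange, if it happened.** In Table 2 each treatment occurs once in every period and once in every sequence. With complete data and equal numbers per sequence, the B minus A estimate is therefore the plain difference of treatment means. Let δ = ln(true B/A). Suppose one of n participants received A and B exchanged and the data were labelled as assigned. Then n − 1 participants contribute δ and one contributes −δ:

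estimate = [(n − 1)δ − δ]/n = δ(1 − 2/n).

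- n = 8: factor 1 − 2/8 = 0.750
- n = 12: factor 1 − 2/12 = 0.833

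The documents state no expected ratio, so the true values below are assumptions.

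| Assumed true B/A | Estimate, n = 8 | Estimate, n = 12 |
|---|---|---|
| 0.70 | 0.70^0.750 = 0.765 | 0.70^0.833 = 0.743 |
| 0.80 | 0.80^0.750 = 0.846 | 0.80^0.833 = 0.830 |
| 1.25 | 1.25^0.750 = 1.182 | 1.25^0.833 = 1.204 |

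A least-squares fit of participant, period and treatment effects to noise-free data on the Table 2 sequences gave the same shrinkage factors.

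**4. When an as-received rule would matter.** There are three cases.

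- *No exchange.* The planned estimate is valid and a rule changes nothing.
- *An exchange nobody detects.* The analyst knows only the assigned treatment, so as assigned and as received are the same data set. A rule again changes nothing.
- *A detected exchange.* Protocol 8.4.10 puts all medication errors on a dedicated CRF page, covers uses outside what the protocol foresees, and requires the sponsor to be told of a dosing error within 24 hours. The analyst then knows which product was given. The shrinkage in step 3 arises only if the data are nevertheless analysed under the wrong label.

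**5. Controls before dosing.** Protocol 6.1.1 and 6.3 have doses given by the randomisation schedule. Protocol 6.2.1 has two operators prepare labelled unit-dose containers. Protocol 6.5 requires a second qualified person to confirm preparation from bulk, the step at which picking up the wrong lot would be caught; the bedside check comes later. Protocol 6.2 requires accountability records.

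**The case for a change.** The strongest reply is that none of these controls names the lot for each participant and period, so an exchange could escape all of them, and a CRF lot field would cost little. The medication-error wording lists wrong participant, time and strength; an A/B exchange has the right participant and strength and is caught mainly by the broader clause. In an open-label study it is also better to fix the handling of wrong-product PK data before anyone sees results. SAP 5.3.2 excludes parameters known to be biased, but its example is vomiting, so as assigned, as received and excluded can all be read into the text.

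All of that is accurate as description. What remains is missing detail. Protocol 6.5 does not claim to list every CRF field, and Protocol 10.1.6 leaves CRF completion to a separate document. In a study whose sole primary purpose is to compare formulations, an analyst told that a participant took B would not report the concentrations as A; the safety-set sentence already shows the sponsor's convention. The missing PK sentence is also not specific to the shared DMID: it would apply equally to an A/C or A/D mix-up.

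The DMID question stands as a question. B may legitimately share the reference's code, and the explanation may be in blacked-out text. The availability sentence covers only the new formulations and points to Table 2, which settles them. The mention in Protocol 2.3 of three or four test formulations is a leftover; the objectives and design use three.

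**Conclusion.** No change is needed. As written, B versus A is a valid comparison of lot 23-DP-01526 with lot 23-DP-01449, and no planned estimate, interval or sample size is affected. The shrinkage of 25% (n = 8) or 17% (n = 12) on the log scale is hypothetical. It assumes one exchange, complete balanced data and analysis as assigned; nothing in the documents suggests that an exchange will occur. If there is none, or if a known one is analysed by product received, the effect is zero. The silence on lot in the dosing record and on product received in the PK sets is a gap that site staff and analysts would fill sensibly. The availability sentence and the count in Protocol 2.3 are clerical. Why A and B share DP-006067 can be asked of the sponsor, but the visible text shows no misidentification.

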2.3. Benefit/Risk Assessment

PF-07817883 is not expected to provide any clinical benefit to healthy participants. The purpose of this study is to estimate the rBA of PF-07817883 in 3 to 4 test tablet formulations relative to reference tablet formulation in healthy adult participants under fasted condition.

More detailed information about the known and expected benefits and risks and reasonably expected AEs of PF-07817883 may be found in the current IB, which is the SRSD for this study. Refer to the Study Intervention(s) table in Section 6.1 for a complete description of SRSDs.

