4.2. Scientific Rationale for Study Design

This study will evaluate bioavailability of 3 new tablet formulations (test) of PF-07817883 relative to the current formulation (reference) in healthy participants.

Based on the median half-life of hr, observed in C5091008 study, which also used 300 mg immediate release tablet formulation as a SD; the hr washout interval is deemed sufficient to provide the concentration <5% of C_{max} in the subsequent period.

In study C5091001, administration of PF-07817883 oral suspension with high-fat meal decreased AUC_{last} and C_{max} by and %, respectively. Thus, to avoid the potential effect of food on PF-07817883 PK, the participants will be dosed in fasted state in all periods.

Drug product acceptability questionnaire is an exploratory endpoint to inform the future product development.

Based in the formulation, the test and reference formulations are expected to have a very similar safety profile. In order to limit the study-burden to a participant, post-dose safety labs/ECG are not proposed in each period.

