Appendix 1. PK Analyses – Example of SAS Code for mixed effects model

An example of the PROC MIXED code:

```
proc mixed data=tab.pk method=reml;
class seq period trt participant;
model &var=seq period trt/ residual ddfm=KR;
random participant(seq);
Ismeans trt;
estimate 'B vs A' trt -1 1 0 0 /cl alpha=0.1;
estimate 'C vs A' trt -1 0 1 0 /cl alpha=0.1;
estimate 'D vs A' trt -1 0 0 1 /cl alpha=0.1;
run;
```

Appendix 2. Categorical Classes for ECG and Vital Signs of Potential Clinical Concern Categories for QTcF

Degree of Prolongation	Mild (ms)	Moderate (ms)	Severe (ms)
Absolute value	>450-480	>480-500	>500
Increase from baseline		30-60	>60

Categories for PR and QRS

PR (msec)	max. ≥300	
PR (msec) increase from	Baseline >200 and max. ≥25%	Baseline ≤200 and max.
baseline	increase	≥50% increase
QRS (msec)	max. ≥140	
QRS (msec) increase from	≥50% increase	
baseline		

Categories for Vital Signs

Systolic BP (mm Hg)	min. <90	
Systolic BP (mm Hg) change from baseline	max. decrease ≥30	max. increase ≥30
Diastolic BP (mm Hg)	min. <50	
Diastolic BP (mm Hg) change from baseline	max. decrease ≥20	max. increase ≥20
Supine pulse rate (bpm)	min. <40	max. >120

Measurements that fulfill these criteria are to be listed in the report.

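### Do the shared material identifier of A and B, the one mention of up to four test formulations, and the undecided-formulations sentence leave the primary comparisons undefined?

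*Protocol*

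**What the plan says.** Protocol Table 2 defines the reference as "Treatment A = PF-07817883 300 mg reference formulation, fasted, DP-006067, 23-DP-01449" and the first test product as "Treatment B = PF-07817883 300 mg test formulation 1, fasted, DP-006067, 23-DP-01526". Treatments C and D have their own DMIDs, DP-006973 and DP-006974. The same assignment appears in the schema legend (Protocol 1.2: "A: DP-006067, 23-DP-01449 B: DP-006067, 23-DP-01526"), in the study-arm table of Protocol 6.1 ("DP-006067, 23-DP- 01526" for B), and in SAP 2.3, Table 2 and Figure 1.

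On the number of test products, Protocol 4.2 says "This study will evaluate bioavailability of 3 new tablet formulations (test) of PF-07817883 relative to the current formulation (reference) in healthy participants". Protocol 1.1, 2.1 and 4.1 and SAP 2.3 agree on three. Protocol 2.3 alone describes the purpose as to "estimate the rBA of PF-07817883 in 3 to 4 test tablet formulations relative to reference tablet formulation".

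Protocol 4.1, just above Table 2, also says "The new formulations used for each treatment as defined in Table 2 will be decided based on the availability of new formulations". SAP 2.3 repeats that sentence.

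The SAP analyses the treatments by letter, for example "estimate 'B vs A' trt -1 1 0 0 /cl alpha=0.1" in Appendix 1, with A as reference and B, C and D as tests.

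**The concern.** The study is meant to inform the choice of formulation for later trials (Protocol 2.1), and B/A is one of its three test-to-reference comparisons. If B were a second lot of the reference product, B/A would measure lot-to-lot difference. If B is a new formulation, B/A measures a formulation effect. The same estimate and interval would be read differently in the two cases, and the visible text does not say how B differs from A.

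The other two statements add to the doubt. Four tests plus a reference make five treatments, which a four-period square cannot hold. A sentence saying the formulations are yet to be chosen, beside contrasts named only by letter, could be read as leaving open which product stands behind each primary ratio. Neither document visibly says what happens to the sequences or contrasts if a formulation is unavailable.

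**Working it through.** **Identifiers (Protocol Table 2; SAP Table 2)**

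| Treatment | Role | DMID | Lot |
|---|---|---|---|
| A | reference | DP-006067 | 23-DP-01449 |
| B | test 1 | DP-006067 | 23-DP-01526 |
| C | test 2 | DP-006973 | 23-DP-01687 |
| D | test 3 | DP-006974 | 23-DP-01696 |

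There are four treatments, four distinct lots and three distinct DMIDs. The lot alone separates every pair of treatments, including A and B. The abbreviation list (Protocol 10.9) expands DMID as dosage material identification and gives no rule that one DMID means one formulation. The entry for B is the same wherever it is printed, and B is labelled test formulation 1 each time. A shared DMID is therefore compatible with a wrong entry, a second lot of one material, or a variant filed under the same identifier. The visible text cannot separate these, and the labelling favours a genuine test product.

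**Number of treatments**

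The sequences are ABCD, BDAC, CADB and DCBA.

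- Distinct letters: 4, that is 1 reference + 3 tests. This reproduces the stated three.
- Each treatment appears once in each period, and each of the 4 × 3 = 12 ordered pairs of neighbouring treatments occurs once.
- Randomised: 4 sequences × 3 = 12. Evaluable: 4 × 2 = 8. Both match Protocol 9.5.
- SAP Appendix 1 has three ESTIMATE statements, each with four treatment coefficients, so there is no place for a fifth treatment.

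The range in Protocol 2.3 therefore conflicts with every operative part of the plan. Nobody could run or analyse five treatments from these documents.

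**Whether the products are fixed**

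The protocol version cited by the SAP is dated 24 August 2023 and the SAP 22 November 2023 (SAP 1). The SAP carries the same four DMIDs and lots as the protocol and records no modifications (SAP 2.1). The contrast letters are tied to lots in SAP Table 2, so replacing a product would make that table wrong and could not pass without a change to the text.

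**Effect on the analysis**

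With participant, period and treatment effects and 12 completers, the variance of each test-minus-A contrast, in units of the within-participant variance, is 2/12 = 0.1667. It depends on the layout of the letters and not on their DMIDs. Correcting the identifier, changing the range to three, or deleting the undecided-formulations sentence leaves the model, contrasts and intervals as they are. The within-participant standard deviations and the Table 4 entries are redacted, so the planned interval widths cannot be reproduced, but they do not bear on this point.

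**The case for a change.** The strongest case for a change is that the undecided-formulations sentence stands in both documents, and the SAP repeats it three months after the protocol. If a formulation were unavailable, sites and analysts would have no written rule.

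The cost of that can be bounded for one missing test product, assuming 12 completers and least squares with participant, period and treatment effects.

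- If its period is left empty, the variance of each remaining test-minus-A contrast stays at 0.1667, a standard-error ratio of 1.00.
- If the periods are closed up, one remaining treatment is given 6, 0 and 6 times in Periods 1 to 3. Contrasts involving it have variance 0.2083, so the ratio is √(0.2083/0.1667) = 1.118, a 12% larger standard error. If C is the one missing, that treatment is the reference, and both remaining contrasts are affected.

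The arithmetic is sound, but nothing in the plan proposes closing up the periods. The plain response, omitting the dose, loses no precision on the other contrasts. The REML mixed model (SAP 5.2.3) takes incomplete participants, and the PK parameter set needs data from only one treatment period (SAP 4). Changes to the study design made by protocol amendment need ethics approval before they take effect (Protocol 10.1.1).

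It also stands that a reader of the public documents cannot tell what B/A isolates. Figures and text have been removed from the biopharmaceutics and rationale sections (Protocol 2.2.4.1 and 4.2), so the explanation may exist in the full protocol. A gap of that kind cannot be counted against the plan. B/A is in any case a valid estimate for the lot dosed.

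**Conclusion.** No change to the design or analysis follows. The three textual observations are correct: A and B share a DMID, one sentence in Protocol 2.3 gives a range where everything operative says three, and one sentence in Protocol 4.1 and SAP 2.3 treats as open what Table 2 fixes. The second and third look like leftover wording. The first is not shown to be an error, since the lots differ and no visible rule says a DMID identifies a single formulation.

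The effect on the planned model, contrasts and 90% intervals is nil. This assumes that the four listed lots are the ones dosed, and that the report describes product B by what it is, which the sponsor knows even if the public text does not show it. The sponsor could tidy the two sentences and confirm B's DMID when the documents are next revised, but the conclusions do not depend on it.
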